8.3.4 Follow-up of subjects after adverse events

If an adverse event/adverse reaction occurs, the Investigator will institute support and/or treatment as deemed appropriate. If a non-serious adverse event/adverse reaction is unresolved at the time of the last visit, efforts will be made to follow up until the adverse event/adverse reaction is resolved or stabilized, the subject is lost to follow-up, or there is other resolution to the event.

9 Statistics

9.1 Primary Hypotheses

As this is only a safety study, there is no planned inferential hypothesis in this study for efficacy.

9.2 Sample Size Considerations

The size of this study is driven by the minimal safety exposure required for an eventual regulatory marketing application.

9.3 Analysis populations

For this safety study, there is no Per-protocol (PP) population. Three other explicit populations are listed here, although they may be effectively synonymous in this single dose safety study.

Randomized Population: The randomized population will include all subjects who were randomized to treatment. Baseline (screening) variables and demographic characteristics will be summarized for this population.

Intent-to-Treat Population (ITT): The ITT population will include all randomized subjects who have received at least one dose (2 drops) of study medication. The ITT population will include subjects as randomized.

Safety Population: The safety population will include all randomized subjects who have received at least one dose (2 drops) of study medication. This population will be used to summarize the safety variables and will summarize subjects as treated.

9.4 Statistical methods to be employed

9.4.1 General Considerations

All continuous study assessments will be summarized by treatment and time point (as applicable) using descriptive statistics (n, mean, median, standard deviation, minimum, and maximum). All categorical study assessments will be summarized by treatment and time point (as applicable) using frequency counts and percentages.

All study data will be listed by treatment, subject, time point, and eye (as applicable).

Statistical methods will be more fully described in a separate document (Statistical Analysis Plan).

9.4.2 Interim analyses

There is no planned interim analysis.

9.4.3 Analysis of Baseline Data

Demographic and baseline characteristics such as age, sex, ethnicity, race, and iris color will be summarized and listed. Depending upon the extent of medical and ocular history and concomitant medications in these healthy subjects, coding systems such as MedDRA and WHODrug will be used, and these data will be summarized and listed.

9.4.4 Subject Disposition

Subject enrollment and exit status (completed or discontinued) will be summarized and listed.

9.4.5 Protocol Deviations

Important protocol deviations are deviations from the protocol that potentially could have a meaningful impact on study conduct, or on the primary efficacy or key safety outcomes for an individual subject. The criteria for identifying important protocol deviations will be defined within the appropriate protocol-specific document. Important protocol deviations will be reviewed as part of the ongoing data cleaning process and all important deviations will be identified and documented prior to unmasking to confirm exclusion from analysis sets. Further details will be provided in the SAP.

9.4.6 Analysis of Efficacy

Not applicable.

9.4.7 Analysis of Safety

Intraocular pressure, slit lamp biomicroscopy, external eye exam, intraocular pressure and cardiovascular measures will be summarized at each measured time point using discrete summary statistics.

Visual Acuity data will be summarized at each time point using both continuous summaries (Logarithmic Minimum Angle of Resolution, logMAR), including change from baseline, and discrete summaries, including change from baseline in the number of lines and the proportion of subjects with a worsening of ≥ 3 lines from baseline.

9.4.8 Adverse Events

Verbatim descriptions of AEs will be mapped to MedDRA thesaurus terms and be presented in a data listing. Treatment emergent AEs, those that occur after the first dose of study medication, will be summarized by treatment group using frequency counts and percentages for each system organ class (SOC) and preferred term (PT) within each SOC. Summaries will be presented separately for ocular and non-ocular AEs. These summaries will also be presented by the relationship to the Investigational Medical Product (related, unrelated) and by severity of the AE (mild, moderate, severe). Fisher's exact test will be used to test the difference in proportions of subjects with each AE between treatment groups (SOC and PT).

9.5 *Procedure for accounting for missing, unused, or spurious data*

For this safety study, only observed data will be used. This is no planned method for imputation of missing data.

9.6 *Procedure for reporting deviations from the statistical plan*

Any deviations from the statistical plan will be described and a justification given in the final statistical report.

9.7 *Data listings*

Data listings will be prepared for all data on the database.

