1.1 Findings from nonclinical and clinical studies

1.2 Potential Risks and benefits to human subjects

Minimal risks are expected with AG-920. Based upon clinical trials conducted to date, expected risks for subjects may include temporary, mild conjunctival/ocular hyperemia, eye pain, instillation site reaction (stinging/burning), and conjunctival hemorrhage. upon instillation of the investigational medicinal product (IMP). For any additional information on AG-920 use, please refer to the [Investigator's Brochure](#).

As this study is to be conducted in healthy subjects, there is no anticipated benefit other than the possibility that a subject's participation in the present study may help others in the future to have more options for local anesthesia before ophthalmic procedures.

Any new, unexpected adverse events (AEs) present among subjects in this clinical trial will be communicated to Investigators and to ethics committees or Institutional Review Board (IRBs) in accordance with local regulations.

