2.5 Sample Size Estimation

The study is intended to enroll a total of 240 subjects in a 2:1 ratio of 160 subjects for AG-920 treatment and 80 subjects for placebo. This sample size is driven by the minimal safety exposure required for a regulatory marketing application.

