5.3 Adverse Events

An overall summary of AEs reported in this study will be provided in Table 4.1.1 for study participants and in Table 4.1.2 for the safety population. The incidences of subjects reporting pre-treatment AE will be reported in Table 4.2.1 for the pre-randomization period and in Table 4.2.2 for the treatment-emergent AEs by treatment. Those treatment-emergent AE by preferred terminology that are reported by more than 5% of subjects in any individual treatment group will be tabulated in Table 4.2.3.

Incidences of subjects reporting treatment-emergent AEs (TEAEs) will also be tabulated by treatment for the TEAEs associated with the study eye in Table 4.2.5 and for the TEAEs associated with fellow eye in Table 4.2.6.

Incidences of subjects reporting treatment-emergent AEs will also be tabulated by onset time (on-treatment day vs. off-treatment day) in Table 4.3.1 for all TEAEs, and in Table 4.3.2 for the TEAEs associated with the study eye, and in Table 4.3.3 for the TEAEs associated with the fellow eye.

The severity of the treatment-emergent AEs and the relationship to the investigational product will be summarized in Table 4.4.1.

Treatment-emergent AEs associated with early terminations and serious AEs will be summarized by preferred term, respectively, in Table 4.4.2 and Table 4.4.3 for all TEAEs, in Table 4.4.4 and Table 4.4.5 for the TEAEs associated with the study eye, and in Table 4.4.6 and 4.4.7 for the TEAEs associated with the fellow eye.

Details of AEs associated with both study and fellow eyes will be listed for each subject (Listing 6)

Details of AEs associated with early terminations will be listed for each subject (Listing 7). SAEs, including deaths, will be listed (Listing 8).

Narratives will be presented for all deaths, non-fatal serious adverse events, and subjects withdrawn due to adverse events.

Female pregnancy results will be listed (Listing 9).

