6 REFERENCES

Study Protocol No. AG920-CS303 version 1.0.

7 List of Statistical Table Shells

Statistical table shells are provided after the text portion. Table shells are presented only for those tables with a unique format. Tables with duplicate formats are indicated in the list of tables below. Final TFL sets will be numbered with the ICH E3 title as listed below.

Table Title (SAP)	ICH E3 Title for Section 14 (TFL)
Table 1.1.1 Screening Summary	Table 14.1.1.1
Table 1.1.2 Enrollment Summary: Randomized population	Table 14.1.1.2
Table 1.1.3 Randomized Treatment Summary: Safety population	Table 14.1.1.3
Table 1.1.4 Randomized Complete Treatment Summary: ITT population	Table 14.1.1.4
Table 1.1.5 Specular Microscopy (SM) Summary: SM population	Table 14.1.1.5
Table 1.2.1 Demography: Randomized population	Table 14.1.2.1.1
Table 1.2.2 Demography: Safety population	Table 14.1.2.1.2
Table 1.2.3 Demography: ITT population	Table 14.1.2.1.3
Table 1.2.4 Demography: SM population	Table 14.1.2.1.4
Table 1.3.1 Baseline Eye Characteristics: Safety population	Table 14.1.2.2.1
Table 1.3.2 Baseline Eye Characteristics: ITT population	Table 14.1.2.2.2
Table 1.3.3 Baseline Eye Characteristics: SM population	Table 14.1.2.2.3
Table 1.4.1 Disposition: Safety population	Table 14.1.3.1
Table 1.4.2 Disposition: ITT population	Table 14.1.3.2
Table 1.5.1 Protocol Deviations: Safety population	Table 14.1.6.1
Table 3.1.1 Treatment Exposure of All Applications (including active and placebo): Safety population	Table 14.1.3.3
Table 4.1.1 Overall Summary of Adverse Events: Randomized population	Table 14.3.1.1
Table 4.1.2 Overall Summary of Adverse Events: Safety population	Table 14.3.1.2
Table 4.2.1 Incidence of Pre-Treatment AEs by Preferred Terminology	Table 14.3.1.3
Table 4.2.2 Incidence of Treatment-Emergent AEs by Preferred Terminology	Table 14.3.1.4
Table 4.2.3 Treatment-Emergent AEs with >5% Subjects Reporting by Preferred Terminology	Table 14.3.1.5
Table 4.2.4 Incidence of Subjects Reporting Post-Treatment AEs by Preferred Terminology	Table 14.3.1.6
Table 4.2.5 Incidence of Subjects Reporting Study-Eye Treatment-Emergent AEs by Preferred terminology	Table 14.3.1.7
Table 4.2.6 Incidence of Subjects Reporting Fellow Eye Treatment-Emergent AEs by Preferred terminology	Table 14.3.1.8
Table 4.3.1 Incidence of Treatment-Emergent AEs and Onset Time	Table 14.3.1.9
Table 4.3.2 Incidence of Study Eye Treatment-Emergent AEs and Onset Time	Table 14.3.1.10

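### The >5% adverse-event table is cut per preferred term with no prespecified grouped term, so a redness or discomfort reaction coded to several terms gets no combined rate and can miss the table

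*Protocol*

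**What the plan says.** Protocol 9.4.8 sets the counting levels. Treatment-emergent events "will be summarized by treatment group using frequency counts and percentages for each system organ class (SOC) and preferred term (PT) within each SOC". It adds that "Summaries will be presented separately for ocular and non-ocular AEs", repeats the tables by relationship and by severity, and applies Fisher's exact test at SOC and PT level.

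SAP 5.3 sets the frequency cut: "Those treatment-emergent AE by preferred terminology that are reported by more than 5% of subjects in any individual treatment group" go into Table 4.2.3. The list of table shells (SAP 7) titles that table "Treatment-Emergent AEs with >5% Subjects Reporting by Preferred Terminology". Table 4.2.2 (all treatment-emergent events) and Table 4.2.5 (study eye) are also by PT but carry no cut.

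Protocol 1.2 gives the local reactions expected from earlier trials: "expected risks for subjects may include temporary, mild conjunctival/ocular hyperemia, eye pain, instillation site reaction (stinging/burning), and conjunctival hemorrhage".

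SAP 2.5 plans "a total of 240 subjects in a 2:1 ratio of 160 subjects for AG-920 treatment and 80 subjects for placebo". Protocol 9.2 explains the basis: "The size of this study is driven by the minimal safety exposure required for an eventual regulatory marketing application".

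The visible text of either document defines no grouped term lying between a single PT and a whole SOC.

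**The concern.** Protocol 1.2 describes redness as either conjunctival or ocular, and discomfort as either eye pain or stinging and burning at the instillation site. Subjects with much the same experience could therefore be coded to different PTs. The cut in Table 4.2.3 is then applied to each fragment separately.

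Ocular safety is the primary objective. For discomfort, AE reporting is the only measure, because neither document lists a discomfort scale. If the reaction is split, nobody reads off the proportion of AG-920 subjects with redness, or with discomfort, and each Fisher comparison with vehicle is made on a fraction of the events. The PT rows cannot be added up to recover the rate, because one subject may appear in more than one. The SOC and ocular rows do not isolate it either, since they also include other eye events.

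**Working it through.** **Inputs from the documents.** 160 AG-920 and 80 placebo (SAP 2.5); cut of more than 5% per PT in either arm (SAP 5.3); Fisher's exact test (Protocol 9.4.8).

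**Assumed inputs.** The number of PTs and the split between them; one PT per subject; a true AG-920 rate of 10%; two-sided testing.

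**The plan's own figure.** The sample size follows from an exposure requirement, with no alpha, power or event rate, so it cannot be re-derived. The allocation is consistent: 240 × 2/3 = 160 and 240 × 1/3 = 80.

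**Step 1: the cut in subjects.** 5% of 160 is 8, and 8/160 = 5.0% is not above 5%, so a PT needs at least 9 AG-920 subjects. 5% of 80 is 4, so it needs at least 5 on placebo.

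**Step 2: how many can stay out of the table.** With k terms and one term per subject, at most 8k AG-920 subjects: 16 (10%) for two terms, 24 (15%) for three, 32 (20%) for four.

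**Step 3: how likely a miss is at a true 10% rate.** Ungrouped, let N ~ Binomial(160, 0.10) be spread over the terms; the table is missed if every term has 8 or fewer. Grouped, it is missed only if N ≤ 8. These figures take no vehicle events; vehicle rates up to 5% change them by less than 0.04.

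| Coding of the reaction | Chance of missing Table 4.2.3 |
|---|---|
| One grouped term | 0.02 |
| Two terms, 70/30 | 0.19 |
| Two terms, equal | 0.34 |
| Three terms, 50/30/20 | 0.56 |
| Three terms, equal | 0.75 |

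**Step 4: a worked example.** Suppose 16/160 on AG-920 and 1/80 on vehicle have redness, and the AG-920 subjects split 8 and 8 over two PTs.

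| Row | AG-920 | Vehicle | Fisher p | In Table 4.2.3? |
|---|---|---|---|---|
| First PT | 8/160 = 5.0% | 1/80 | 0.279 | No |
| Second PT | 8/160 = 5.0% | 0/80 | 0.055 | No |
| Grouped | 16/160 = 10.0% | 1/80 = 1.25% | 0.014 | Would enter |

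The grouped difference is 10.0 − 1.25 = 8.75 points (Newcombe 95% CI 2.1 to 14.5).

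**Step 5: how special that example is.** Given exactly 16 subjects and two terms, only an exact 8/8 split misses the cut; at 9/7 the larger term is 9/160 = 5.6% and enters. The chance of 8/8 is 0.20 under random 50:50 coding and 0.05 under 70:30. When the larger term does enter, its row still shows less than the 10% of subjects affected.

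**Step 6: effect on the comparison.** For assumed rates of 10% against 2.5%, Fisher's test at two-sided 0.05 has power 0.54 on the grouped counts and 0.17 on each PT if the events divide evenly over two terms.

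**The case against.** The strongest reply is that little is hidden. Tables 4.2.2 and 4.2.5 have no cut, so both 5.0% rows would be printed there. No success criterion depends on Table 4.2.3. Counting and testing are also done by SOC, and the ocular summaries are repeated for related events, which in a single-dose study of healthy subjects may come close to the group wanted. This stands, and it limits the point to a missing combined rate.

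The split is also an assumption. The documents give no coding frequencies, Protocol 8.3 asks for a diagnosis rather than symptoms where one is available, and inconsistent data are queried (Protocol 10.4). These measures may reduce splitting. They do not say how to choose between conjunctival and ocular hyperemia, or between pain and stinging.

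Conjunctival hyperemia is also graded at the slit lamp. However, that exam is 60 to 90 minutes after dosing, while the expected reactions are called temporary, and the SAP analyses a total over seven items, which is not a rate of redness.

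Two stronger readings are tempting and should not be drawn:

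- A reader might infer that events are counted only by single PT. Protocol 9.4.8 counts and tests by SOC as well; only the cut is PT-only.
- A reader might infer that the protocol expects one reaction under several names. Protocol 1.2 lists several risks and does not call them one. Redness and discomfort are different, and hemorrhage is a separate sign.

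Finally, the table shells themselves are not in the text available, so a grouped row there cannot be excluded.

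**Conclusion.** The point holds as a gap in the planned tables. It does not show that the tabulation is wrong or that events would disappear. As written, no visible row gives the proportion of subjects with redness or with instillation discomfort, and the comparison with vehicle is not made at that level.

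Under the coding splits examined, a reaction with a true 10% rate would miss the >5% table with probability from about 0.19 (70/30) to 0.75 (three equal terms), against about 0.02 if grouped. The 8/8 example is the two-term worst case and should be read as such. All of this assumes that such events are coded to more than one PT, with one PT per subject. If they all fall under one PT the problem does not arise, and subjects coded to several PTs would make a miss less likely.

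**What to change.** Before unmasking, fix a short list of PTs for two groups drawn from Protocol 1.2:

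- **Ocular redness:** the conjunctival and ocular hyperemia terms.
- **Instillation discomfort:** the eye pain, stinging, burning and instillation-site reaction terms.

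Count each subject once per group. Add the two group rows to Tables 4.2.2 and 4.2.5 above their component PTs. Apply the >5% rule of Table 4.2.3 and the planned Fisher comparison to the groups as well as to the PTs. Keep every PT row as planned.

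The cost is two extra rows per table and agreement on the term list, which is the only real effort. Fixing the list before unmasking also avoids any suggestion that the groups were chosen from the results.

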2 OBJECTIVES AND ENDPOINTS

Primary Objective	Primary Endpoints
To evaluate the ocular safety of a single dose of AG-920 after topical ocular administration of Articaine Sterile Topical Ophthalmic Solution (2 drops 30 seconds apart)	Visual acuity, intraocular pressure, biomicroscopy, AEs, TEAEs, SAEs, withdrawals due to TEAEs
Secondary Objectives	Secondary Endpoints
A subset of up to 20 subjects (with expectations that 12 receiving AG-920 and 6 receiving vehicle) will undergo specular microscopy prior to and 3 months after receiving masked study medication to evaluate the effect of AG-920 on corneal endothelial cell count (ECC).	Mean change from baseline in corneal endothelial cell density after treatment with AG-920

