2.9.3 Safety analysis

Treatment Exposure

Frequencies of exposure to the study medication will be calculated based on the number of drops the subject has received over the course of the study. Frequencies of exposure will be categorized as the following: 1 drop and 2 drops. Frequencies of exposure will be summarized by treatment for the safety population defined in Section 3.1, as well as by gender.

Compliance rates will be calculated by dividing the number of drops received by the number of drops that should have been given during the application of dose. Compliance rates will be summarized.

Early Termination

Subject disposition will be summarized by treatment and will be listed for those subjects who are terminated early. This listing will include demographic variables, treatment assigned, number of drops received, termination date, and the primary reason for early termination.

Adverse Events

Adverse events will be coded for preferred terminologies using Medical Dictionary for Regulatory Activities (MedDRA). AEs will be grouped into pre-treatment AE, treatment-emergent AE, and post-treatment AE and will be reported separately, based upon the start date and time of the events and the start date and time of the treatment.

Adverse events will be defined as pre-treatment AEs if they occur prior to the treatment start date and time; as treatment-emergent AEs if they occur on or after the treatment start date and time and before the next day; and as post-treatment AEs if they occur after the treatment date.

Frequency of treatment-emergent AEs will be calculated for each body system, by preferred terminology, by treatment group, for number of subjects and percentage reporting the event. The severity of the adverse events and the relationship to the investigational product will be summarized for each body system and preferred terminology by treatment group. Withdrawals due to adverse events will be summarized for each body system and preferred terminology by treatment group and will be listed with demographic variables for individual subjects.

Serious adverse events (SAE) (including deaths) will be listed for individual events.

Narratives will be provided for all deaths, non-fatal serious adverse events, and subjects withdrawn due to adverse events.

Best Corrected Visual Acuity (BCVA)

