BCVA will be summarized in logMAR units by treatment for the screening (pre-dose) and Day 1 (post-dose), using number of observations, mean, standard deviation, minimum, median, and maximum values. The analysis will be based on the safety population defined in [Section 3.1](#).

For both study eye and fellow eye, changes in BCVA at post-dose from screening (pre-dose) will be analyzed for differences between AG-920 and placebo groups, using analysis of covariance (ANCOVA), with the pre-dose measurement as the covariate. Any BCVA changes of >3 lines from baseline will be flagged.

Intraocular Pressure (IOP)

Mean or median IOP values observed at a time point will be summarized in mmHg units by treatment for the screening (pre-dose) and Day 1 (post-dose), using number of observations, mean, standard deviation, minimum, median, and maximum values. The analysis will be based on the safety population defined in Section 3.1. Subjects who participated in the specular microscopy subset will also have IOP measured at Visit 3.

IOP measurements can be performed using a Tonopen® or Goldmann Tonometer. If a Goldmann tonometer is used, then two consecutive IOP measurements of each eye will be obtained. If the two measurements differ by more than 2 mm Hg, a third measurement should be obtained. IOP will be analyzed as the mean of two measurements or as the median of three measurements.

For both study eye and fellow eye, changes in IOP at post-dose from screening (pre-dose) will be analyzed for differences between AG-920 and placebo groups, using analysis of covariance (ANCOVA), with the pre-dose measurement as the covariate.

Biomicroscopy (Slit Lamp)

Total severity scores of biomicroscopy (slit lamp of seven items on grading scale, including lid erythema, lid edema, conjunctiva hyperemia, conjunctiva edema, corneal edema, anterior chamber cells, and anterior chamber flare) will be summarized and analyzed individually by treatment for the screening (pre-dose) and Day 1 (post-dose), and Visit 3 (for specular microscopy subjects) using number of observations, mean, standard deviation, minimum, median, and maximum values. The analysis will be based on the safety population defined in [Section 3.1](#).

For both study eye and fellow eye, changes in the total severity score at post-dose from screening (pre-dose) will be analyzed for differences between AG-920 and placebo groups, using analysis of covariance (ANCOVA), with the pre-dose measurement as the covariate.

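### The protocol promises a Fisher's exact comparison of each AE between arms; the visible SAP text gives only counts and percentages and does not say why

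*Protocol*

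**What the plan says.** Protocol 9.4.8 commits to a between-arm test for adverse events: Fisher's "exact test will be used to test the difference in proportions of subjects with each AE between treatment groups", at both SOC and PT level. Section 2 of the protocol lists the primary endpoints as "Visual acuity, intraocular pressure, biomicroscopy, AEs, TEAEs, SAEs, withdrawals due to TEAEs". Section 9.4.1 leaves the fuller description of statistical methods to the SAP.

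SAP 2.9.3 handles the same data descriptively: "Frequency of treatment-emergent AEs will be calculated for each body system, by preferred terminology, by treatment group", as numbers and percentages of subjects. Severity and causality are likewise summarised, not compared. SAP 5.3 continues in that way: "Incidences of subjects reporting treatment-emergent AEs (TEAEs) will also be tabulated by treatment", followed by listings and narratives.

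For BCVA, IOP and the slit-lamp total score, the same SAP section goes further. Changes from screening "will be analyzed for differences between AG-920 and placebo groups, using analysis of covariance (ANCOVA"). Protocol 9.4.7 mentions no such test for these measures.

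**The concern.** The SAP should be at least as specific as the protocol. On AEs it is less specific: the one between-arm test that the protocol's statistics section names does not appear in the visible SAP, while tests that the protocol does not name have been added for other safety measures. Nothing in the visible text treats this as a decision.

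The vehicle arm is there so that AEs can be judged against it. SAP 1.1 frames the objective with reference to placebo, and SAP 3.1 makes the safety population primary for comparative safety analyses. A programmer working from the SAP text alone would produce two columns of percentages with nothing to show how precisely their difference is known. An interval method chosen after unmasking, or a decision then on how much weight the p-values carry, would be open to the criticism that it was made with the results in view.

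**Working it through.** **Step 1: the two texts side by side.**

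- Test for AEs. Protocol 9.4.8: Fisher's exact, per SOC and PT. SAP 2.9.3 and 5.3: none named; no p-value, confidence interval or risk difference.
- Abbreviations. The SAP list defines CMH and CI, but the visible text uses neither.
- Table titles (SAP section 7). The BCVA, IOP and biomicroscopy tables are titled as summary and analysis; the by-term AE tables are titled as incidence. This agrees with the methods text: analysis for the former, tabulation for the latter.
- Explanation. The visible SAP gives none.
- Not visible: the shells, which SAP section 7 places after the text. They could carry a p-value column.

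**Step 2: which events a comparison would count.** Protocol 8.3 treats every AE after the first dose as treatment-emergent, up to the follow-up call (Day 2-5) or, for the specular microscopy subset, Visit 3 at about 90 days. SAP 2.9.3 ends the treatment-emergent period with the dosing day and calls later events post-treatment. Those later events go to Table 4.2.4, which is in the table list but not in the 5.3 text. SAP 5.3 also splits TEAEs into on- and off-treatment-day onset (Tables 4.3.1 to 4.3.3), which its own definition leaves no room for. A Fisher column added only to Tables 4.2.2, 4.2.3 and 4.2.5 would therefore test dosing-day events, not the protocol's set.

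**Step 3: arm sizes.** From 240 at 2:1 (SAP 2.5): 240 × 2/3 = 160 and 240 × 1/3 = 80, as stated. The size is exposure-driven, and no alpha, power or AE rate is given. Everything below assumes two-sided 0.05 and invented event counts.

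**Step 4: illustration, 8/160 against 0/80.**

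- Difference: 8/160 − 0/80 = 0.050.
- Wilson 95% limits: 0.0256 to 0.0956 for AG-920; 0 to 0.0458 for placebo.
- Newcombe lower limit: 0.050 − √[(0.050 − 0.0256)² + (0.0458 − 0)²] = −0.002.
- Newcombe upper limit: 0.050 + √[(0.0956 − 0.050)² + (0 − 0)²] = 0.096.
- Fisher, two-sided, conditional on 8 events in 240 subjects: the chance of 0 on placebo is C(160,8)/C(240,8) = 0.0367. The outcomes no more likely than this are 6, 7 or 8 on placebo (0.0158 + 0.0021 + 0.0001). The total is p = 0.055.

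One more AG-920 event (9/160 against 0/80) gives p = 0.031, the smallest significant count against zero. With a commoner event, 21/160 against 4/80 gives p = 0.071 and CI −0.3 to 14.9 points; 22/160 gives p = 0.047.

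**Step 5: what the test alone can do.** Exact power at 160 against 80, for assumed placebo and AG-920 rates:

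- 5% and 10%: 20.5%
- 5% and 15%: 64.1%
- 10% and 20%: 48.4%
- 10% and 25%: 80.4%

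With k independent terms each tested at 0.05, the chance of at least one false positive is at most 1 − 0.95^k: 40% for 10 terms and 64% for 20. Fisher's test is conservative (exact size 3.4% when both rates are 5%), so the true figures are lower.

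**The case against.** The strongest reply is that the two documents together do not lose the test. The SAP is silent on Fisher's test; it does not revoke it. Protocol 9.4.8 still stands, and running the test later would carry out the protocol. A reader might infer that the AE endpoint is left with raw percentages only, or that a Fisher analysis run after unmasking would be post hoc. The documents support neither. The first describes only the visible SAP text, and the unseen shells might add to it. The second is wrong because the protocol pre-specifies the test. What would be post hoc is a choice made after unmasking of interval method or of the status of the p-values.

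Nor does any success criterion depend on an AE p-value. AEs are one of several listed primary endpoints, and none has a stated hypothesis, alpha or power. Protocol 9.1 disclaims inference, though only for efficacy, so it does not cancel the AE test. Counts per arm will be reported, so anyone can compute a difference and interval from them. Neither document promises a confidence interval for AEs; that is a recommendation.

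Finally, the 8/160 example shows the weakness of a p-value read alone, which is a criticism of the protocol's test and not a measure of what the SAP omits. That is right. It argues for putting an interval beside the test, and it is why removing the test with a stated reason is an acceptable way to reconcile the documents.

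What survives is the conflict itself: a test named in one document, absent without explanation from the visible text of the other, and no stated measure of uncertainty for AE differences.

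**Conclusion.** The point holds as an unreconciled difference between protocol and SAP that should be corrected before unmasking. It rests on the visible text; if the shells carry a Fisher column, the gap shrinks to missing methods wording, a missing interval and the TEAE window.

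It is not evidence that the trial cannot compare AEs between arms. The documents supply no AE rates, so the practical size cannot be estimated. On the assumed counts, a term at 5.0% against 0% would be non-significant at two-sided 0.05 while its interval still allows an excess of almost 10 points. That shows why percentages alone, or a p-value alone, would be hard to interpret. It does not predict what the trial will find.

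**What to change.** Before unmasking:

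1. Check the table shells for any AE comparison.
2. Reconcile the TEAE definitions in Protocol 8.3 and SAP 2.9.3. Apply the comparison to all post-dose AEs under the protocol definition, including those that the SAP now sends to Table 4.2.4, and not only to Tables 4.2.2, 4.2.3 and 4.2.5.
3. In SAP 2.9.3 and 5.3, specify for each SOC and PT the AG-920 minus placebo risk difference with a 95% CI, naming the method (Newcombe or exact). Beside it, give the protocol's two-sided Fisher p-value, labelled nominal and unadjusted for multiplicity. Alternatively, record that the Fisher test is removed, with the reason, and keep the interval.
4. State that a non-significant result is not evidence of no difference.

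The cost is SAP wording and extra columns in tables that are already planned; no new data are needed. The small downside is a long run of nominal p-values, some of which will fall below 0.05 by chance. The label deals with that.
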